5.3. Lifestyle Considerations

Participants must not donate blood for the duration of the study and for 8 weeks following the study.

5.4. Screen Failures

A screen failure occurs when a participant who consents to participate in the clinical study is not subsequently randomly assigned to study intervention. A minimal set of screen failure information is required to ensure transparent reporting of screen failure participants to meet the Consolidated Standards of Reporting Trials (CONSORT) publishing requirements and to

respond to queries from regulatory authorities. Minimal information includes demography, screen failure details, eligibility criteria, and any SAE.

Individuals who do not meet the criteria for participation in this study (screen failure) may be rescreened 1 time and require a new identification number. If initial MRI image needs to be resubmitted, it will not cause a new identification number to be submitted. If, in the opinion of the investigator, an ineligible laboratory test result is the result of an error or extenuating circumstance, then that parameter can be retested once without the participant having to be rescreened.

The interval between screenings should be at least 1 week.

5.5. Criteria for Temporarily Delaying Enrollment of a Participant

This section is not applicable for this study.

6. Study Intervention(s) and Concomitant Therapy

Study intervention is defined as any investigational intervention(s), marketed product(s), placebo, or medical device(s) intended to be administered to, or used by, a study participant according to the study protocol.

6.1. Study Intervention(s) Administered

Each participant will receive either placebo or LY3561774 via subcutaneous injection.

Intervention Name	LY3561774	Placebo
IMP and NIMP	IMP	IMP
Authorized as defined by EU Clinical Trial Regulation	No	No
Use	Experimental	Placebo-control
Dose Form	Solution	Solution
Unit Dose Strength(s)	200 mg/mL	Not applicable
Dosage Level(s)	100 mg 400 mg 800 mg	Not applicable
Route of Administration	Subcutaneous injection	Subcutaneous injection
Sourcing	Provided centrally by the sponsor	Commercially available 0.9% sodium chloride solution.
Labeling	Study intervention will be labeled as appropriate for country requirements.	

Abbreviations: IMP = investigational medicinal product; NIMP = non-investigational medicinal product.

This table describes the number of injections for the different intervention dose groups.

Intervention group	Number of injections
100 mg or matched placebo participants	1 injection
400 mg or matched placebo participants	1 injection
800 mg or matched placebo participants	2 injections

Location of subcutaneous injections

All SC injections will be administered into the SC tissue of the abdominal wall, 5 to 10 cm from the umbilicus.

If multiple injections are needed, they will be performed in quick succession and each injection should be delivered into separate quadrants in the anterior abdominal wall.

Record the package number and location of each injection.

6.2. Preparation, Handling, Storage, and Accountability

The investigator or designee must confirm appropriate storage conditions have been maintained during transit for all study intervention received and any discrepancies are reported and resolved before use of the study intervention.

All study intervention must be stored in a secure, environmentally controlled, and monitored (manual or automated) area in accordance with the labeled storage conditions with access limited to the investigator and authorized study personnel.

The investigator or authorized study personnel are responsible for study intervention accountability, reconciliation, and record maintenance (that is, receipt, reconciliation, and final disposition records).

Only authorized study personnel may supply, prepare, or administer study intervention.

Only participants enrolled in the study may receive study intervention.

Further guidance and information for the final disposition of unused study interventions are provided in the Pharmacy Manual.

6.3. Measures to Minimize Bias: Randomization and Blinding

Randomization

All participants will be centrally assigned to randomized study intervention using an IWRS. Before the study is initiated, the log in information and directions for the IWRS will be provided to each site.

Participants will be randomly assigned in a 2:1:2:2 ratio to placebo: LY3561774 100 mg:400 mg:800 mg. Placebo participants will be randomly assigned so that each dose cohort will have a matching placebo cohort that receives the same dose volume to maintain the study blind.

Participants will be stratified according to the Visit 1 TG level of <250 mg/dL and \geq 250 mg/dL.

Maintaining blinding

Investigators will remain blinded to each participant's assigned study intervention within each dose group, throughout the course of the study. To maintain this blind, an otherwise unblinded third party will be responsible for the receiving, registering, preparing, and administering of all study intervention. Although the participant and the investigator will know the injection volume, they will not know whether the participant is receiving LY3561774 or placebo. To mitigate the risk of unblinding due to color difference between IMPs, site will be trained on additional operational procedures. Unblinded personnel who administer IMP to participants at Visit 2 will have no other interaction, role, or responsibilities other than receiving, registering, preparing, and administering IMP at Visit 6 in the trial. Participants should be instructed to look away during IMP administration.

Emergency unblinding

The IWRS will be programmed with blind-breaking instructions. In case of an emergency, the investigator has the sole responsibility for determining if unblinding of a participant's intervention assignment is warranted. Participant safety must always be the first consideration in making such a determination.

If a participant's intervention assignment is unblinded, the sponsor must be notified immediately within 24 hours of this occurrence. The date and reason that the blind was broken must be recorded.

Discontinuation from the study in case of unblinding

If an investigator, study personnel performing assessments, or participant is unblinded, the participant must be discontinued from intervention and follow procedures outlined in Section 7.1. In cases where there are ethical reasons to have the participant remain in the study, the investigator must obtain specific approval from a sponsor clinical research physician for the participant to continue in the study.

6.4. Study Intervention Compliance

Study intervention will be administered under medical supervision by the investigator or designee. The study intervention and study participant identification will be confirmed prior to the time of dosing. The date and time of each dose administered will be recorded in the source documents and in the CRF.

6.5. Dose Modification

This protocol does not allow dose adjustments.

6.6. Continued Access to Study Intervention after the End of the Study

Study intervention will not be available to participants after completion of the study.

6.7. Treatment of Overdose

The sponsor does not recommend specific treatment for an overdose.

In the event of an overdose, the investigator should

- contact the medical monitor immediately
- evaluate the participant to determine, in consultation with the medical monitor, whether study intervention should be interrupted, and
- closely monitor the participant for any AE/SAE and laboratory abnormalities until LY3561774 no longer has a clinical effect.

6.8. Concomitant Therapy

See Section 10.7 for lists of medications that are permitted or prohibited in this study.

Concomitant therapy regimens

All participants should maintain their usual medication regimens for concomitant conditions or diseases throughout the study, unless those medications are specifically excluded in the protocol.

Participants taking concomitant medications should be on stable dosages at the time of screening and should remain at stable dosages throughout the study, unless changes need to be made because of AEs.

Changing concomitant therapy

Participants should consult with authorized study personnel before taking any new medications or supplements during the study. Authorized study personnel should consult the sponsor's medical monitor if there are any questions about concomitant therapies during the study.

The investigator or the participant's usual diabetes care physician is responsible for changes in diabetic medications.

Concomitant therapy data collection

For therapy that the participant is receiving at the time of enrollment or receives during the study, authorized study personnel should collect

- the name of medication, vaccine or therapy
- the reason for use, and
- dates of administration, including start and end dates.

For diabetes and lipid modifying medications, such as statins and PCSK9 inhibitors, collect dosage information including dose and frequency.

7. Discontinuation of Study Intervention and Participant Discontinuation/Withdrawal

Discontinuation of specific sites or of the study as a whole are handled as part of Section 10.1.9.

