2.2. Background

A detailed description of the chemistry, pharmacology, efficacy, and safety of LY3561774 is provided in the IB.

Clinical Study EZCA preliminary results

Study J3F-MC-EZCA (EZCA) is a first-in-human study of LY3561774, assessing the safety, tolerability, PK, and PD of single-ascending subcutaneous and repeat subcutaneous doses of LY3561774 in participants with dyslipidemia. The study had 3 parts that are described in this table.

Study EZCA Part	Subcutaneous dosing frequency	Dose levels	Number of participants at data cut-off date for preliminary results
A	Single	24, 72, 208, 480 and 960 mg	40
B	2 doses given 28 days apart	208 or 480 mg	16
C	Single	208 or 480 mg	18 Japanese participants ^a

^a Part C was a cohort of only Japanese participants.

Safety

Preliminary results suggest LY3561774 is generally well tolerated when administered as single doses up to 960 mg and as 2 doses of either 208 or 480 mg.

Treatment emergent adverse events were mostly mild in severity.

Part A

Treatment emergent adverse events reported by at least 2 participants included headache, increased blood creatine phosphokinase, and rash.

After single doses, transient elevations of liver enzymes (AST or ALT >2x ULN) and/or creatine kinase (>5x ULN) were observed. These were not associated with any clinical signs or symptoms.

All ISRs resolved spontaneously and there was no apparent relationship of the frequency or severity with the dose.

Part B

Treatment emergent adverse events reported by at least 2 participants included headache, increased hepatic enzymes, and rash.

No clinically relevant changes in laboratory values were observed.

Injection-site reactions were reported after administration of 1 dose or repeat dosing, and they spontaneously resolved with no apparent relationship to dose.

Part C

Treatment emergent adverse events reported by at least 2 participants included ecchymosis.

One participant had ALT >2x ULN, but less than 3x ULN with no associated clinical signs or symptoms.

Injection-site reactions were reported by 4 participants.

Pharmacokinetics

Part A

After single doses, LY3561774 PK across the tested dose range exhibited

- linear PK
- median t_{max} between 7.5 and 12.5 hours, and
- mean terminal half-life from 5.5 to 12.9 hours.

Part B

After 2 doses, LY3561774 PK exhibited

- approximate dose proportionality across the dose range tested
- consistent PK with single-ascending dose cohorts

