Abbreviations: AE = adverse event; ANGPTL3 = angiopoietin-like protein 3; Apo = apolipoprotein; FG = fasting glucose; HbA1c = hemoglobin A1c; HDL-C = high-density lipoprotein-cholesterol; hsCRP = high-sensitivity C-reactive protein; LDL-C = low-density lipoprotein-cholesterol; MRI = magnetic resonance imaging; SAE = serious adverse event; TEAE = treatment emergent adverse event; UACR = urinary albumin/creatinine ratio; and VLDL-C = very-low-density lipoprotein-cholesterol.

Primary estimand

The primary clinical question of interest is

What is the treatment difference in ApoB percent change from baseline after 180 days of treatment in participants who meet the inclusion criteria and would have completed the treatment period?

Efficacy estimand attributes

This table describes the efficacy estimand attributes.

Efficacy Estimand Attribute	Description
Population	Participants who meet the inclusion criteria. Further details can be found in Sections 5 and 9.
Endpoint	Percent change from baseline in ApoB at Day 180.
Treatment condition	The randomized treatment.
Population-level summary	Difference in mean percent changes in ApoB at Day 180 between LY3561774 and placebo.

Intercurrent events

The intercurrent events including the following are handled by the hypothetical strategy:

- Permanent discontinuation of intervention.
- Initiation of excluded medications taken during the study.
- New initiation of any lipid-lowering drug required to be on a stable regimen prior to treatment per the protocol inclusion criteria.

The potential outcome of interest is the response in the efficacy measurement if participants adhere to the randomized treatment.

Rationale for the efficacy estimand

This Phase 2 study aims to study the efficacy of LY3561774 under the ideal condition that all participants adhere to the randomized treatment.

Estimand(s) for secondary objectives

The same estimand for the primary objective will be used for the secondary clinical response endpoints.

Unless specified otherwise, safety assessments will be guided by an estimand comparing safety of LY3561774 doses with placebo irrespective of adherence to study intervention, including data collected during the treatment period and safety follow-up.

4. Study Design

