5.1. Inclusion Criteria

Participants are eligible to be included in the study only if all of the following criteria apply:

Age

1. Must be 18 years of age or older at the time of signing the informed consent.

Type of participant and disease characteristics

2. Have fasting TGs within the range of 150 to 499 mg/dL (1.69 to 5.64 mmol/L) at screening.
3. Have fasting LDL-C \geq 70 mg/dL (1.81 mmol/L) at screening.
51. Have fasting non-HDL-C \geq 130 mg/dL (3.36 mmol/L) at screening.
4. Must be on a stable moderate or high-intensity dose of a statin (See Section 10.7.1) for at least 2 months before screening and remain on the same medication and dose for the duration of the study.

Weight

5. Have a body mass index within the range of 18.5 to 40.0 kg/m², inclusive.

Sex and contraceptive/barrier requirements

6. Are WOCBP who agree to use contraception as outlined in Section 10.4 or
Are WNOCBP as defined in Section 10.4 or
Are men who agree to use contraception as outlined in Section 10.4.

Contraceptive use by participants should be consistent with local regulations regarding the methods of contraception for those participating in clinical studies.

Definitions and contraception requirements for participants in this study are provided in Section 10.4.

Informed consent

7. Are capable of giving signed informed consent as described in Section 10.1.3, which includes compliance with the requirements and restrictions listed in the ICF and in this protocol.

Other inclusions

8. Have not started a structured weight loss program within 3 months of screening, or plan on starting a program during the study.
9. If taking hypertensive therapy, doses must be stable 30 days prior to screening.
10. Are reliable and willing to make themselves available for the duration of the study and are willing to follow study procedures.
11. Have an optimal MRI image quality at screening, as assessed by central laboratory.

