10.7. Appendix 7: Concomitant Medication Information

10.7.1. ACC/AHA Statin Therapy List

This table describes different types of statin therapy by intensity according to the American College of Cardiology and the American Heart Association (ACC/AHA) rating system (Stone et al. 2014).

High-Intensity Statin Therapy	Moderate-Intensity Statin Therapy
Daily dose lowers LDL-C by approximately $\geq 50\%$	Daily dose lowers LDL-C by approximately 30% to $< 50\%$
Atorvastatin 40 mg, 80 mg Rosuvastatin 20 mg, 40 mg	Atorvastatin 10 mg, 20 mg Rosuvastatin 5 mg, 10 mg Simvastatin 20 mg, 40 mg Pravastatin 40 mg, 80 mg Lovastatin 40 mg Fluvastatin XL 80 mg Fluvastatin 40 mg BID Pitavastatin 2 mg, 4 mg

Simvastatin 80 mg is not allowed in this study.

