Abbreviations: ADA = anti-drug antibodies; AE = adverse event; ANGPTL3 = angiopoietin-like protein 3; Apo = apolipoprotein; ApoA-I = apolipoprotein A-I; ApoB = apolipoprotein B; ApoC-III = apolipoprotein C-III; FG = fasting glucose; HbA1c = hemoglobin A1c; HDL-C = high-density lipoprotein-cholesterol; hsCRP = high-sensitivity C-reactive protein; LDL-C = low-density lipoprotein-cholesterol; MRI = magnetic resonance imaging; SAE = serious adverse event; TEAE = treatment-emergent adverse event; TG = triglycerides; UACR = urinary albumin/creatinine ratio; VLDL-C = very-low-density lipoprotein-cholesterol.

Primary estimand

The primary clinical question of interest is: what is the treatment difference in the apolipoprotein B (ApoB) percent change from baseline after 180 days of treatment in participants who meet the inclusion criteria and who would have completed the Study EZCB treatment period?

The "efficacy estimand" is described by

- population: participants who meet the inclusion criteria; further details can be found in Sections 5 and 9 of the Study EZCB protocol
- endpoint: percent change from baseline in ApoB at Day 180, and
- treatment condition: the randomized treatment, without any excluded medications or additional lipid-lowering drugs.

The intercurrent events for Study EZCB are permanent discontinuation of intervention, initiation of excluded medications taken during the study, and new initiation of any lipid-lowering drug required to be on a stable regimen prior to treatment per the protocol inclusion criteria. These are handled by a hypothetical strategy wherein the potential outcome of interest is the participant's response in the efficacy measurement, if participants had adhered to the randomized treatment.

The potential outcomes related to the efficacy estimand are summarized at the population level using the difference in mean percent changes in ApoB at Day 180 between each dose of LY3561774 and placebo.

The rationale for this estimand is to study the efficacy of LY3561774 under the ideal condition that all participants adhere to the randomized treatment.

Estimand(s) for secondary objectives

The same estimand for the primary objective will be used for the efficacy endpoints for the secondary objective of comparing the clinical response of each dose of LY3561774 to placebo.

Secondary estimand: treatment-regimen estimand

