2.1. Multiplicity Adjustment

All treatment comparisons will be performed at the full significance level of 0.05. No adjustment for multiplicity will be performed.

3. Analysis Sets

This table defines the analysis population and datasets for the purposes of analysis.

Population	Description
Screened	All participants who signed informed consent.
Randomized	All participants who are randomly assigned to a treatment arm.
EAS	Data obtained during the treatment period from all randomly assigned participants who are exposed to at least 1 dose of the study intervention and are not discontinued due to inadvertent enrollment. Excludes data after any of
	 permanent discontinuation of intervention initiation of excluded medications taken during the study, and new initiation of any lipid-lowering drug required to be on a stable regimen prior to treatment per the protocol inclusion criteria.
	Participants will be included in the treatment group to which they were randomly assigned.
FAS	Data obtained during the treatment period from all randomly assigned participants who are exposed to at least 1 dose of study intervention, regardless of adherence to intervention, and are not discontinued due to inadvertent enrollment. Participants will be included in the treatment group to which they were randomly assigned.
SAS	Data obtained during the treatment period plus safety follow-up from all randomly assigned participants who are exposed to at least 1 dose of the study intervention, regardless of adherence to the intervention, and are not discontinued due to inadvertent enrollment. Participants will be included in the treatment group to which they were randomly assigned.

Abbreviations: EAS = efficacy analysis set; FAS = full analysis set; SAS = safety analysis set.

4. Statistical Analyses

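### Stopping or re-dosing a baseline lipid-lowering drug is not an intercurrent event, so ApoB measured afterwards stays in the primary analysis

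*Protocol*

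**What the plan says.** **Background therapy.** Inclusion criterion 4 (Protocol 5.1) requires a stable moderate- or high-intensity statin and that participants "remain on the same medication and dose for the duration of the study". It states no exception for adverse events. Protocol 6.8 says that concomitant medications "should remain at stable dosages throughout the study, unless changes need to be made because of AEs", and does not exempt the statin. Ezetimibe, PCSK9 inhibitors and bempedoic acid are also permitted (Protocol 10.7.2).

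**Intercurrent events.** Protocol Section 3 leaves its list formally open: "The intercurrent events including the following are handled by the hypothetical strategy". SAP 1.1 closes it: "The intercurrent events for Study EZCB are permanent discontinuation of intervention, initiation of excluded medications taken during the study", and, as the third event, "new initiation of any lipid-lowering drug required to be on a stable regimen prior to treatment per the protocol inclusion criteria". The treatment condition in SAP 1.1 is "the randomized treatment, without any excluded medications or additional lipid-lowering drugs".

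**Data rule.** The EAS definition (SAP 3) and the primary analysis (SAP 4.3) cut a participant's data only at one of these events. SAP 4.1 counts anyone who received both doses as on treatment for the whole treatment and assessment period.

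**The concern.** Each listed event is either an end to study drug or the start of another drug. Removing or re-dosing a lipid-lowering drug that the participant already takes is neither. ApoB responds to that change, and the MMRM would read the response as an effect of the randomized arm.

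The plan appears to want a stable background. Its third event refers to drugs that must be on a stable regimen under the inclusion criteria, which for lipid-lowering drugs means the statin of criterion 4. Yet the event is triggered only by an initiation.

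The direction of any bias depends on which arm has more changes. Protocol 2.2 reports that after single doses in Phase 1 "transient elevations of liver enzymes (AST or ALT >2x ULN) and/or creatine kinase (>5x ULN) were observed". Such findings could lead to a change in the statin. If that happened more often on active treatment, ApoB in those arms would rise and the contrast would move toward no effect. The study is meant to inform dose decisions (Protocol 2.1), so effect size and dose-response matter as well as significance.

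**Working it through.** **1. Which rule would cut the data?**

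| Event | Cut from the EAS? |
|---|---|
| Study drug permanently discontinued before the second dose | Yes |
| Excluded medication started, including simvastatin 80 mg/day | Yes |
| Switch to a different statin | Arguably, as a new initiation |
| Baseline statin stopped, or dose of the same statin changed (other than to simvastatin 80 mg/day) | No |
| Permitted ezetimibe, PCSK9 inhibitor or bempedoic acid stopped or re-dosed | No |

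Dosing is on Day 0 and Day 90 only. After the second dose there is no further dose to discontinue, and SAP 4.1 keeps the participant on treatment. A statin stop between Day 90 and Day 180 therefore does not by itself remove the Day 180 value.

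**2. The plan's own power figure.** Inputs from Protocol 9.5: 175 participants, 2:1:2:2, 20% dropout, SD 15, difference -30, two-sided alpha 0.05.
- Completers: 175 × 2/7 × 0.8 = 40; 175 × 1/7 × 0.8 = 20.
- SE, 20 vs 40: 15 × √(1/20 + 1/40) = 4.11. SE, 40 vs 40: 15 × √(2/40) = 3.35.
- Power = Φ(30/SE − 1.96): Φ(5.34) and Φ(6.98). Both exceed 99%, as stated.

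**3. Shift in the estimate.** The documents give neither a rate of statin withdrawal nor an ApoB rebound, so both are assumed. A fraction f stops completely and stays off to Day 180, and ApoB in those participants is multiplied by g. Protocol 10.7.1 says of moderate-intensity statins: "Daily dose lowers LDL-C by approximately 30% to" less than 50%; for high intensity it gives about 50% or more. If ApoB moved like LDL-C, g = 1/0.7 = 1.43 at 30% lowering and 1/0.5 = 2.0 at 50%. A milder g = 1.2 is added as an assumption.

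The SAP analyses log values, so estimate = 0.70 × exp[(f_active − f_placebo) × ln g] − 1.

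| f active vs placebo | g = 1.2 | g = 1.43 | g = 2.0 |
|---|---|---|---|
| 5% vs 0% | -29.4% | -28.7% | -27.5% |
| 10% vs 0% | -28.7% | -27.5% | -25.0% |
| equal rates | -30.0% | -30.0% | -30.0% |

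Example: 0.70 × exp(0.05 × ln 2) = 0.70 × 1.0353 = 0.725. Five percent is 1 of 20 or 2 of 40 completers.

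**4. Precision.** Log-scale SD = √[s² + f(1 − f)(ln g)²] with f = 5%. The plan gives 15% on the percent scale only.
- If s = 0.15, the SD becomes 0.17 (g = 1.43) or 0.21 (g = 2.0).
- If the 15 points apply at a mean ratio of 0.70, s = 0.15/0.70 = 0.21, and the SD becomes 0.23 or 0.26.

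**5. Power with the shift (percent scale).** At a true -30% and 5% vs 0%, power stays above 99% for every g. The lowest value found at 10% vs 0% is 95.8% (100 mg arm, g = 2.0).

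For an assumed smaller effect of -15% at 100 mg, power without stopping is Φ(15/4.11 − 1.96) = 95.5%. With 5% vs 0%:
- g = 1.2: difference 100 × (0.85 × 1.01 − 1) = -14.15; SE = √(238.7/20 + 225/40) = 4.19; power about 92%.
- g = 1.43: difference 100 × (0.85 × 1.0215 − 1) = -13.2; SE = √(288.5/20 + 225/40) = 4.48; power 83.7%.

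**The case against.** **The estimand does not require a stable background in words.** Its stated ideal is adherence to randomized treatment, and the SAP rules out only excluded and additional drugs. This stands in part: the strategy for this event is a choice. But the SAP makes no explicit choice. Its default retains the values, which sits poorly with the third event's reference to a stable regimen.

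**Imbalance is not shown.** A reader might infer that statin changes will be more frequent on active treatment. The documents do not support that. Protocol 2.2 calls the elevations transient and without clinical signs or symptoms, reports no clinically relevant laboratory changes in Part B, and gives no placebo rates. This objection stands in full.

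**Sites are blinded.** Results that could unblind are not reported to sites (Protocol 10.2). Lipid results are withheld after randomization, as is ApoB except at Day 270, so a lipid-driven statin increase on placebo is largely closed off. This stands; the point rests on AE-driven changes.

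**Other rules catch some cases.** Step 1 of the check shows which. It would be too strong to say that all later data are always kept.

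**The effect is small.** At 5% vs 0% the shift of 0.6 to 2.5 points is below one standard error of the contrast (3.4 or 4.1 points), and it is conservative. This stands for the superiority test.

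**The plan partly covers it.** The FAS analysis (SAP 4.5.2) follows a treatment-policy strategy, and concomitant medications and important deviations are summarized by arm (SAP 6.4, 6.5). However, the FAS answers a different question, and a table of drugs taken does not show stops or dose changes.

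**Criterion 4 and 6.8 may be a rule and its exception.** That reading is possible, but neither passage refers to the other.

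**Conclusion.** The gap is real and limited. Followed as written, the SAP keeps ApoB values obtained after an AE-driven change in baseline lipid-lowering therapy, and after Day 90 no other rule reliably removes them.

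If 5% of an active arm and no placebo participants stopped a statin completely to Day 180, a true -30% would be estimated at about -29.4% to -27.5% for rebounds of 1.2 to 2.0. These are illustrations: the rate, the duration, the rebound and the ApoB/LDL-C equivalence are all assumed, and partial dose changes are not quantified. With equal rates only the variance rises.

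A reader might infer that the primary superiority claim is at risk or exaggerated. It is not: imbalance toward active treatment pulls the estimate toward no effect, and power at -30% stays above 95% in every case checked. What can suffer is effect size, precision and dose-response, especially at 100 mg, with about 20 completers and a dose chosen for low efficacy (Protocol 4.3). The change should be made.

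**What to change.** - Add to the intercurrent events in Protocol Section 3, SAP 1.1, SAP 3 (EAS) and SAP 4.3: discontinuation of, or change in dose of, any lipid-lowering drug taken at baseline (statin, ezetimibe, PCSK9 inhibitor, bempedoic acid). Use the same hypothetical strategy, so that data after the change are excluded from the EAS.
- Tabulate these changes by arm, with timing relative to Day 90 and Day 180.
- Keep the FAS treatment-regimen analysis, which retains the data, as the companion.
- Reconcile inclusion criterion 4 with Protocol 6.8. This review takes no position on which clinical rule should apply.

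Cost: one derivation, one table, SAP wording and a small edit to protocol text. Start and end dates, and dose and frequency for lipid-modifying drugs, are already collected (Protocol 6.8). The downside is that a few more values leave the EAS, and the MMRM relies on missing at random for them.
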